### **6.2.3 Participant recruitment**

Patients who are prescribed Feraccru® and eligible for inclusion in the study will be identified by their care team and approached and asked to provide consent to allow their

medical records to be used in the study. There will be no change to the management of patients as a result of taking part in the study. No additional patient investigations or tests will be required. In order to maximise the number of eligible patients, there will be two methods of patient identification and consent;

1. Retrospective recruitment - Patients who were initiated on Feraccru® since its launch in June 2016 will be approached and asked to complete a consent form either by post or when they return to the gastroenterology clinic for routine follow-up visits.
2. Prospective recruitment - Patients initiated on Feraccru® during the study period will be identified and asked to provide consent (and complete a consent form) at the time of Feraccru® initiation.

The study will recruit approximately 100 patients across 5 centres.

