## **8. Study sample size**

Given the descriptive nature of this study, a preliminary estimation of the required sample size is expressed in terms of precision and not statistical power. In the literature, the percentage of patients treated with Feracceu® with reported normalised Hb at 12 weeks is approximately 66%. However, the accuracy of such estimates will vary according to the number of participants in the study. Using 66% as the percentage of patients expected to show a normalised Hb at 12 weeks, the precision of such estimates can be calculated using a Binomial confidence interval (Table 2).

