## **9. Statistical analysis**

Analyses will be performed by pH Associates. The planned analysis will be descriptive in nature. Both distributions and descriptive statistics of central tendency (arithmetic means and medians) and dispersion (standard deviation, interquartile range) will be presented for quantitative variables. Nominal variables will be described with frequencies, percentages and modes, while ordinal variables will also have medians and interquartile ranges described. Confidence intervals will be provided for means of quantitative variables.

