### **9.1 Missing data**

Whilst study centres will be selected to include those expected to have the most complete data, this study involves the retrospective collection of data from medical records. As such,

it is possible that some data points will be missing. Where data are missing from the original medical record, the affected analyses will be conducted using only the results of those patients with data available (complete case analysis) and the number of patients included in each analysis will be stated. The percentage of data missing will be reported for each study variable. Missing data in itself will be of interest and should provide insight into the way patients are being managed in the UK outside the methodological constraints of a clinical trial.

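### The sample size rests on a binomial confidence interval for the primary percentage, but the analysis section plans no such interval, and complete case is the only handling of a missing week 10–16 Hb

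*Combined protocol and SAP*

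**What the plan says.** The primary endpoint (Section 6.5.1) is binary: Hb normalised or not at 12 weeks, with a window of 10 to 16 weeks.

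Section 8 sizes the study by precision instead of power. Taking 66% as the expected percentage, it says "the precision of such estimates can be calculated using a Binomial confidence interval (Table 2"). The title of Table 2 identifies the interval as Wald. The text below the table, and the synopsis, give a precision of 9–10% for 100 patients without naming a confidence level.

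Section 9 sets out the analysis. For categorical outcomes: "Nominal variables will be described with frequencies, percentages and modes". On intervals: "Confidence intervals will be provided for means of quantitative variables". Neither Section 9 nor the synopsis mentions an interval for a percentage.

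Section 9.1 gives one rule for missing values: "the affected analyses will be conducted using only the results of those patients with data available (complete case analysis"). It adds two mitigations. On centres: "study centres will be selected to include those expected to have the most complete data". On disclosure: "The percentage of data missing will be reported for each study variable", together with the number analysed. No sensitivity analysis appears anywhere.

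Section 6.2.3 states: "No additional patient investigations or tests will be required". The 12-week Hb therefore depends on usual practice.

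**The concern.** The study tests no hypothesis (Section 5), so its main result is the primary percentage and the uncertainty around it. The analysis plan names intervals for means, such as mean change in Hb. It does not name one for the quantity whose interval justified the number of patients. Section 3.1 asks whether trial results are replicated in practice, and a percentage without an interval is a weak basis for answering that.

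The second part concerns who contributes to the percentage. Whether a patient was retested between weeks 10 and 16 may be related to response or to stopping treatment. If it is, the complete-case percentage is biased, and nothing in the plan tests how far the result depends on this. It is better to specify such a check beforehand, since Section 10 plans no independent review of results before the report.

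A smaller point of wording is that the stated precision is tied to 100 recruited patients (Section 6.2.3), whereas Section 9.1 analyses only those with a value.

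**Working it through.** **1. The plan's own figures.** Inputs from Section 8 are p = 0.66 and Wald half-width d. The confidence level is not stated, so two-sided 95% (z = 1.96) is tried.

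n = z² × p(1 − p) / d² = 3.8416 × 0.2244 / d² = 0.8621 / d²

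| d | n before rounding | rounded up | Table 2 |
|---|---|---|---|
| 7% | 175.9 | 176 | 176 |
| 8% | 134.7 | 135 | 135 |
| 9% | 106.4 | 107 | 107 |
| 10% | 86.2 | 87 | 87 |
| 11% | 71.2 | 72 | 72 |
| 12% | 59.9 | 60 | 60 |

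Every row reproduces at 95%. A 90% level does not fit (123.9 at 7%, 60.7 at 10%). The arithmetic of Table 2 is correct.

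**2. Precision per evaluable patient.** Half-width = 1.96 × √(0.2244 / n).

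- n = 100: 9.28 points
- n = 90: 9.79 points
- n = 87: 9.95 points
- n = 86: 10.01 points
- n = 80: 10.38 points
- n = 70: 11.10 points

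The stated 9–10% therefore needs at least 87 patients with an in-window Hb. The loss below that number is small.

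**3. The interval that is not planned.** If 66 of 100 were normalised, the 95% interval would be:

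- Wald: 66 ± 9.28, or 56.7–75.3%
- Wilson: 56.3–74.5%
- exact (Clopper–Pearson): 55.8–75.2%

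The choice of method hardly matters at this size.

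**4. Missing Hb.** The documents give no rate, so the missing shares m are assumptions, with 66% normalised among those observed. The lower bound counts every missing value as not normalised: 0.66(1 − m). The upper bound counts every one as normalised: 0.66(1 − m) + m. A milder assumed case gives missing patients a rate q 20 points lower or higher (46% or 86%): 0.66(1 − m) + q × m.

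| m | extreme bounds | milder case |
|---|---|---|
| 10% | 59.4–69.4% | 64.0–68.0% |
| 20% | 52.8–72.8% | 62.0–70.0% |
| 30% | 46.2–76.2% | 60.0–72.0% |

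At 20% missing, the lower bound lies 66 − 52.8 = 13.2 points below the headline, more than the 9.3-point half-width at 100. At 10% the gap is 6.6 points, which is less. The milder case moves the result by 2, 4 or 6 points, always less than the half-width.

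**5. Windows still open at data cut-off.** Section 6.2.3 also recruits prospectively: "Patients initiated on Feraccru® during the study period will be identified and asked to provide consent" when treatment starts. Table 3 gives May to August 2017 for data collection. Assuming that it ends on 31 August (only the month is given), a start after 22 June 2017 cannot reach week 10, and a start after 11 May 2017 has not completed week 16. Section 9.1 does not separate these patients from those whose window passed without a test.

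Removing everyone whose window was still open would not be a sound correction. A patient who started on 1 June 2017 and had an Hb on 17 August (day 77, week 11) counts in the primary analysis, but the window closes on 21 September (day 112). Dropping that observed value would give bounds that need not contain the primary result.

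**The case against.** The strongest reply has four parts.

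- **An interval can still be given.** Section 9 does not forbid one, and the promised frequencies and number analysed let any reader compute it. Section 16 commits to STROBE reporting, but the checklist's content is not in the documents, so it cannot be relied on to close the gap. A reader might infer that the report will omit the interval. The text supports only that none is planned.
- **Missingness is addressed.** The synopsis says that the 10–16 week window is there to accommodate routine visits. Centres are chosen for completeness. Section 7.2 adds checks, queries and a pilot review, and Section 11 adds feasibility work. All this stands as reducing or disclosing missing values. None of it supplies an Hb that was never measured, or shows how much the result depends on those absent.
- **Complete case is defensible in a descriptive records study, and the harm is hypothetical.** This also stands. A reader might infer that the complete-case percentage will be too high, because patients who stop treatment are not retested. The documents establish neither a missing rate nor a direction, and under the milder assumption the shift is smaller than sampling error.
- **Table 2 already shows precision at smaller N.** It does, so a reading that the study is too small or wrongly sized is not supported. What remains is the unstated confidence level and the link to recruited instead of evaluable patients.

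**Conclusion.** The point holds as a gap in the analysis plan, of minor to moderate weight. As written, no interval is planned for the primary percentage, although an interval for that percentage is the whole justification for the sample size. Complete case is the only stated handling of a missing in-window Hb, and no analysis examines its effect.

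The omission of the interval is certain from the text and does not alter the estimate. The size of any missing-data effect is not known. The bounds in the working rest on assumed missing shares of 10–30% and on 66% among those observed, and they are extremes, not forecasts. The precision point is one of wording only. Nothing here invalidates the design or calls for more patients.

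**What to change.** 1. **Section 9.** State that the primary percentage will be reported with a two-sided 95% binomial confidence interval, and name the method. Wilson or exact would be suitable; Wald would match Section 8.
2. **Section 9.1.** Keep complete case as the main analysis. Add one pre-specified sensitivity analysis on all eligible enrolled patients that keeps every observed in-window Hb. Count a missing Hb as not normalised for the lower bound and as normalised for the upper bound. Report separately how many of the missing had a window still open at the end of data collection, using the initiation date already collected (Section 6.5.3). Optionally repeat the bounds without those patients. Label the results as extreme bounds so that they are not read as a second headline.
3. **Section 8 and synopsis, wording only.** Say that the precision is a 95% half-width and applies per patient with an in-window Hb: 9.3 points at 100, 10.0 at 87 and 10.4 at 80.

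The cost is a few sentences and table rows, with no added patients, tests or variables. The bounds may look wide, and the stated precision becomes slightly less favourable.

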### **9.1 Missing data**

Whilst study centres will be selected to include those expected to have the most complete data, this study involves the retrospective collection of data from medical records. As such,

it is possible that some data points will be missing. Where data are missing from the original medical record, the affected analyses will be conducted using only the results of those patients with data available (complete case analysis) and the number of patients included in each analysis will be stated. The percentage of data missing will be reported for each study variable. Missing data in itself will be of interest and should provide insight into the way patients are being managed in the UK outside the methodological constraints of a clinical trial.

## **10. Review of study results**

No independent review of statistical data/study results is planned prior to completion of the study report. Investigators will be able to review the study results at the investigator meeting.

## **11. Study limitations**

The quality of the dataset may be limited by the accuracy and completeness of patients' medical records. It is believed that this limitation will be minimised by robust feasibility testing of the protocol framework during its development and additional evaluation during site selection. Furthermore, training of all data collectors and source data verification will ensure high quality data and will minimize potential bias.

## **12. Safety**

### **12.1 Definitions**

#### **12.1.1 Adverse events**

An adverse event (AE) is any untoward medical occurrence in a patient administered a pharmaceutical product and which does not necessarily have to have a causal relationship with this treatment. An AE can therefore be any unfavourable and unintended sign (including an abnormal laboratory finding, for example), symptom, or disease temporally associated with the use of a medicinal product, whether or not considered related to the medicinal product. The definition of an AE includes worsening of a pre-existing medical condition.

Adverse drug reactions (ADRs) are a subset of AEs where there is a clear causal relationship between the treatment and the event. This study requires the collation of all AEs, including ADRs.

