### **6.5.3 Variables to be collected**

The following study variables will be collected during the observation period to measure the study endpoints, in order to describe the use of Feraccru® in the real world.

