**Adverse events:**

The details of adverse events (AEs) that are considered to be related to Feraccru® treatment, determined by clinical opinion, will be collected:

- Type, severity, start and end dates of AE/serious adverse event (SAE) with a temporal relationship to and caused by Feraccru®, as determined by the clinician

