## **12.2 Reporting procedures for adverse events**

All SAEs/Special Reporting Situations related to any Shield Therapeutics PLC product(s) at each centre shall be reported to PrimeVigilance Limited by the Principal Investigator /pH Associates within 24 hours of discovery or notification. Initial SAE information and all follow-up information must be recorded on the SAE form and emailed to PrimeVigilance Limited. Investigators may be requested to provide follow-up information concerning serious adverse events, including an evaluation of causality and seriousness. Relatedness of the SAE to Shield Therapeutics PLC product(s) will be assessed by the investigator if there is doubt.

All non-serious AEs will be captured as part of the study dataset and will be tabulated in the study report but will not be subject to expedited reporting. Only SAE and AEs judged to be related to Feraccru® will be included as a study endpoint. As all adverse events will be documented (and ultimately made available to the Medicines and Healthcare products Regulatory Agency, MHRA) by Shield Therapeutics PLC as study sponsor, there is no need for investigator sites to duplicate adverse event reporting through the Yellow Card Scheme.

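### Sections 12.1.1 and 12.2 promise capture of all adverse events, but the only collection list (6.5.3) covers events judged related to Feraccru

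*Combined protocol and SAP*

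**What the plan says.** Section 12.1.1 defines an AE as an untoward occurrence "whether or not considered related to the medicinal product". It counts abnormal laboratory findings and worsening of existing conditions, and then sets the scope: "This study requires the collation of all AEs, including ADRs".

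Section 12.2 makes four statements that bear on scope:
- On capture: "All non-serious AEs will be captured as part of the study dataset and will be tabulated in the study report".
- On the endpoint: "Only SAE and AEs judged to be related to Feraccru® will be included as a study endpoint".
- On reporting within 24 hours: the wording covers serious adverse events (SAEs) and special situations related to a sponsor product.
- On the Yellow Card Scheme: "there is no need for investigator sites to duplicate adverse event reporting through the Yellow Card Scheme". The reason given is that the sponsor will document all adverse events and ultimately make them available to the regulator.

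Section 6.5.3, under its adverse-event heading, says: "The details of adverse events (AEs) that are considered to be related to Feraccru® treatment, determined by clinical opinion, will be collected". The single bullet beneath it asks for type, severity and dates of AEs and SAEs "with a temporal relationship to and caused by Feraccru®, as determined by the clinician". The objectives (4.3) and secondary endpoints (6.5.2) carry the same restriction.

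**The concern.** The safety section is written for all events and the collection list for attributed events. A data collector who works from 6.5.3 has nowhere to put an event that the clinician thought unrelated.

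This matters because tolerability is one of the reasons given for the study (3.1). Section 3 lists bloody diarrhoea, abdominal pain and cramps as symptoms of inflammatory bowel disease. A gastrointestinal event during oral iron treatment can therefore plausibly be put down to the underlying disease, although 12.1.1 would count a worsening of that disease as an AE. Section 6.5.3 also moves from events considered related to events caused by the product, which is a stricter test, so events of uncertain cause may drop out.

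Under related-only capture, the study data would give no overall AE frequency and would not allow a second look at attribution.

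**Working it through.** No arithmetic applies. The check sorts events into four classes and reads off what each section provides for them.

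| Event class | Collated (12.1.1) | On the collection list (6.5.3) | Tabulated (12.2) | 24-hour reporting (12.2) | Endpoint (6.5.2, 12.2) |
|---|---|---|---|---|---|
| Non-serious, related | yes | yes | yes | no | yes |
| Non-serious, unrelated | yes | **not listed** | **yes** | no | no |
| Serious, related | yes | yes | not mentioned | yes | yes |
| Serious, unrelated | **yes** | **not listed** | **not mentioned** | **not covered** | no |

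Section 12.3 adds a route for AEs in its listed special situations (pregnancy, overdose and so on). The table describes events outside those.

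1. **Related events (rows 1 and 3).** Every section that addresses them agrees that they are collected. There is no conflict here.
2. **Unrelated non-serious events (row 2).** Sections 12.1.1 and 12.2 require them in the dataset, and 12.2 requires them in a table. Section 6.5.3 provides no field for them. If the form follows 6.5.3, the 12.2 table would contain related events only and would not be the table promised.
3. **Unrelated serious events (row 4).** Section 12.1.1 requires them to be collated. They are absent from the collection list, the tabulation sentence names only non-serious events, and the reporting wording covers product-related SAEs. No section gives them a general route.
4. **The Yellow Card statement.** Its stated reason is that all adverse events will be documented. Under 6.5.3 that would be accurate for rows 1 and 3 and inaccurate for rows 2 and 4.
5. **The endpoint.** Restricting it to related events is compatible with capturing all events. The difficulty is that the collection list has the scope of the endpoint and not the scope of the capture statement.

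**Size.** If a proportion p of recorded AEs is judged related, a proportion 1 − p would be missing under related-only collection. The documents give no value for p, and putting in an assumed range would only return its complement.

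**The case against.** The strongest reply is that the two scopes can coexist. Section 6.5.3 never says that only related events are to be collected, and it opens by tying its list to the endpoints: "The following study variables will be collected during the observation period to measure the study endpoints". Section 12.2 itself separates wide capture from a narrow endpoint. On this reading 6.5.3 lists endpoint variables, section 12 sets the wider safety capture, and a site that records every AE complies with both. That much stands: the sections are not impossible to follow together. It does not close the gap, because 6.5.3 is the protocol's list of variables to be collected and no other list has fields for unrelated events. The form and the Data Collection Guidelines (section 7) might supply them. Neither is among the documents, so this cannot be checked in either direction.

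Three stronger inferences are tempting, and the documents do not support them:
- **That unrelated events would vanish without trace.** The source is the hospital record (6.4), entries must be traceable to it (15.2), and 10% of patients undergo source data verification (7.2). The events would be missing from the study data but not from the notes. The verification is described as a review of the data collected, so it is not a substitute for collecting the events.
- **That the Yellow Card position rests on data that do not exist.** Related events are documented under either reading, and related SAEs go to the safety provider within 24 hours. The documents do not say what sites would otherwise have sent through the scheme. What fails is the literal premise, and only for unrelated events.
- **That 12.2 promises a table of every AE.** The tabulation sentence is confined to non-serious events.

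**Conclusion.** The point holds as an internal inconsistency in the scope of AE collection. Sections 12.1.1 and 12.2 promise more than 6.5.3 provides for, and unrelated SAEs fall outside the collection list, the tabulation sentence and the general reporting wording.

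The consequences are conditional on the form following 6.5.3. In that case the table of all non-serious AEs cannot be produced, the reason given for the Yellow Card statement is inaccurate, and clinician attribution cannot be re-examined without returning to the notes.

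No numerical magnitude can be given from the documents. The primary endpoint (haemoglobin normalisation) is untouched, and the related-only AE endpoint can be delivered as written. What is affected is the completeness of the safety data and the accuracy of what the protocol says about them.

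**What to change.** Reconcile 6.5.3, 12.1.1 and 12.2, ideally before data collection starts, because events not abstracted can be recovered only by reopening the notes.

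**Preferred.** Extend 6.5.3 so that the form records every AE and SAE found in the notes during the observation period, with type, severity, seriousness, start and end dates, and a clinician relatedness field. Keep the related subset as the endpoint. Produce the table of non-serious AEs that 12.2 promises, and list SAEs alongside it. The cost is more than one added field: the definition in 12.1.1 takes in abnormal laboratory findings and worsening of existing disease, so abstraction in this population will take extra work. The notes are, however, already being reviewed.

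**Alternative.** If related-only capture is intended, narrow the all-AE statements in 12.1.1 and 12.2, and revise the Yellow Card statement so that it no longer rests on all adverse events being documented. This costs only a text change, but the report then has no overall AE frequency and no means of re-examining attribution from the study data.

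Under either option, bring the Data Collection Guidelines into line with the amended text.
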